6.2.2.2 Secondary Efficacy Variables: Sensitivity Analysis

As a sensitivity analysis for the total HF events endpoint, a joint frailty model (Rogers et al., 2016) with constant baseline hazard for CV death and constant baseline intensity for HF events will be fitted including effects for treatment group, pooled region for stratified analyses

and baseline LVEF ($<60\%$, $\geq 60\%$). A gamma frailty distribution will be assumed. This model gives a treatment effect on total HF events which is adjusted for a potential treatment effect on CV death. An effect on CV death might otherwise dilute the effect seen on the hospitalizations, i.e. an effective treatment will prevent CV deaths especially in the more severely ill participants, which then potentially results in many hospitalizations.

The joint frailty model can sometimes have convergence issues (Toenges & Jahn-Eimermacher, 2020); additionally, estimates obtained from the model have sometimes been observed as unstable (e.g., large differences with changes in starting values and/or ordering of covariates in the model). Should such problems be encountered, a simpler model including only treatment group as a fixed effect will be used instead. The joint frailty model additionally produces an estimate for CV death; however, this will be considered only supportive for the analysis of this component and instead the main analysis for the CV death component is described under the primary efficacy variable in Section 6.2.1.2.

6.2.2.3 Secondary Efficacy Variables: Supportive Analysis

As supportive analysis for the total HF events endpoint, stratified Cox proportional hazard regression analyses will be performed for the following endpoints and plots of Aalen-Johansen estimates of the cumulative incidence functions will be provided:

- Time to first HF event
- Time to first HHF
- Time to first urgent HF visit

The additional analyses of the secondary time-to-first event endpoints will include an “on-treatment analysis”. For the renal composite endpoint, events will only be counted if they occur within 5 months after the last visit with complete information on all components of the composite primary endpoint. A 5-month time window is used as visits are 4-monthly and in order to allow for late attendance by an additional 1 month. The proportional hazards assumption will be investigated by plotting smoothed Schoenfeld residuals. For the renal endpoint, a time-to-first event analysis will be done separately for each of the components.

A supportive analysis of the KCCQ TSS will apply a worst-case imputation for death which means that if a patient dies, a worst score of 0 for the TSS will be imputed for all subsequent visits after the patient’s death (i.e., composite strategy). Treatment effects at Month 6, 9 and 12 will also be investigated individually by adding a treatment-by-visit interaction into the model.

A responder analysis for the KCCQ TSS will also be performed, defining patients with an increase of ≥ 5 points from baseline to Month 12 (or, for those with a baseline score of >95 , a score of >95 at Month 12 without decline from baseline) as a responder. All observed values will be included irrespective of any permanent treatment discontinuation. In case of missing data, a patient’s last available post-baseline score prior to Month 12 will be used (i.e. while-alive strategy) unless the patient died before Month 12 in which case they will be imputed as a non-responder (i.e. composite strategy). Responder status will be analysed using a logistic regression model including treatment, baseline TSS and stratification factors as covariates; the odds ratio and associated 95% CI will be reported. This analysis will be repeated for cut-offs of ≥ 10 points increase from baseline to Month 12 (or maintaining a score of >90 from baseline to Month 12 without decrease from baseline) and ≥ 20 points increase (or maintaining a score of >80 without decrease from baseline). These cut-offs correspond to small (≥ 5), moderate (≥ 10) and large (≥ 20) clinically meaningful improvements (Spertus et al, 2005). A

further analysis will define those responders who do not experience a ≥ 5 points decrease from baseline (or, for those with a baseline score of <5 , a score of ≥ 5 at Month 12). This is equivalent to not experiencing a small deterioration. The number and percentage of patients who are responders or non-responders per each of the above criteria will be presented at Months 6, 9 and 12. This will include a breakdown of the criteria met for response (e.g. increase from baseline of ≥ 5 , >95 at baseline and post-baseline visit) or non-response (e.g. change from baseline of <5 , >95 at baseline and ≤ 95 at post-baseline visit, missing score at post-baseline visit).

A second responder analysis for the KCCQ TSS will use the thresholds derived from the anchor-based analyses with the Patient Global Impression of Severity (PGIS) and Patient Global Impression of Change (PGIC) for a clinically meaningful within-patient change in KCCQ TSS at month 6, 9 and 12, respectively, which have been performed separately on blinded data (cf. Section 6.2.3.1). The derived thresholds are

- Minimally important within-patient improvement: 9.09
- Moderate within-patient improvement: 19.85

These thresholds will be used for each timepoint.. All observed values will be included irrespective of any permanent treatment discontinuation. In case of missing data, a patient's last available post-baseline score prior to Month 6, 9 or 12, respectively, will be used unless the patient died before the respective scheduled visit in which case they will be imputed as a non-responder. Responder status will be analysed using a logistic regression model at each timepoint including treatment, baseline TSS and stratification factors as covariates; the odds ratio and associated 95% CI will be reported.

Empirical cumulative density functions will be plotted for Months 6, 9 and 12, with change from baseline in KCCQ TSS (+100 to -100, ordered from greatest possible improvement to greatest possible worsening) on the x-axis and proportion of participants achieving this change or greater on the y-axis. Separate curves will be presented for each treatment group.

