4.5.5 Other Data Handling

Only the data provided by the central laboratory will be used for analysis; values from local laboratories will not be used in the statistical analysis unless otherwise specified and will be listed only. For example, as described above, local values will be used in the derivation of baseline, if no central measurement is available (cf. Section 4.5.1).

At all visits post-randomization and if not stated otherwise, only the values at scheduled measurements will be used for analysis.

For the derived visit “Any time post baseline” (applicable for efficacy) this will include any measurement after randomization, including unscheduled assessments. For the derived visit

“Any time on treatment” (applicable for efficacy), only assessments on or after study medication start date until 30 days after last study drug administration, including unscheduled assessments, will be considered. For safety, “Any time treatment-emergent” will include measurements on or after study medication start date until 3 days after last study drug administration, including unscheduled assessments.

For values which are < LLOQ (Lower limit of quantification), half the value of the LLOQ will be used for analysis. Differences between two values < LLOQ will be assigned values of 0. Ratios between two values < LLOQ will be assigned a value of 1. For values which are > ULOQ (Upper limit of quantification), the ULOQ will be used for analysis.

In case of non-normally distributed data, descriptive statistics other than minimum, maximum and median will only be calculated if at least 2/3 of the individual data were measured and were above the lower limit of quantification. In tables showing descriptive statistics, where values below LLOQ are included, these descriptive statistics will be marked.

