6.2.1.5 Primary Efficacy Variable: Other Supportive Analyses

A supportive analysis of the primary endpoint will exclude urgent HF visits and consider only CV deaths and HHFs as events. Also, an additional analysis of the primary endpoint will restrict CV deaths to HF-related events and thus will consider HF events and CV deaths due to HF. These analyses will both be performed for total (first and recurrent) events and for first events only.

A total-time approach considering times from randomization to the onset of first, second, third composite event using a Wei, Lin, and Weissfeld (WLW, 1989) model will be applied. This model enables analysis of the cumulative effect on the primary endpoint from randomization (i.e. the effect on second event includes the effect on the first, and the effect on third event includes the effects on the first and second). The corresponding individual HRs with 95% CIs comparing treatment groups on the first, second, and third event will be presented.

In addition, a conditional gap-time model according to Prentice, Williams and Peterson (PWP, 1981) will be applied to obtain HR estimates with 95% CIs for the time from first to second and from second to third event (note that this gives a non-randomized comparison). Both models will employ robust standard errors and include the stratification factors and treatment group as fixed effects. Both WLW and PWP approaches are known to have limitations and hence are strictly only performed as supplemental analyses since they aim at describing different aspects of recurrent events.

An “on-treatment” analysis will be performed, including only events occurring up to 30 days after treatment discontinuation. This analysis will be performed in the SAF instead of the FAS.

In addition, table and figure of risk ratios and respective confidence intervals will be provided for the primary efficacy endpoint with patients being censored sequentially at each study day similar to figure 3 in Packer et al. (2021). The first day where the upper CI of the RR is below 1 and stays below for the remainder will be marked.

The primary analysis for the primary endpoint will also be repeated for the “Total HF events and ACM” endpoint.

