7.2 Overview of Changes to SAP – from version 2.0 to version 3.0

Removed reference to older protocol versions.

Clarification of log-normality assumption for specific parameters added.

Specification for the derivation of median for subgroup splits included.

Updated definition of SAF – clarifying exclusion of participants with GCP violation.

Included definition of listing-only participants.

Removed ‘ethnicity’ from demography as not being collected in the study. Included a further category of <90 for SBP categorization, due to respective observed values.

Updated PT Term from ‘Liver cirrhosis’ to ‘Hepatic cirrhosis’.

Restricted some analyses on concomitant medications to medications in the standard drug groups of interest.

Separated CYP3A4 inhibitors and inducers.

Removed analysis of mean daily dose of MRAs due to unclean data.

Included total treatment duration in patient-years.

Removed analyses with continuous covariate of baseline LVEF as well as analysis with time by treatment interaction for primary and secondary endpoints.

Updated definition of ‘on-treatment’ in general and for renal composite endpoint specifically.

Included information on handling time after the forth event for analysis of the first 4 composite events.

Included further imputation rules for secondary endpoint ‘Improvement in NYHA class’.

Rules for usage of covariance patterns in case of non-convergence included for MMRM analysis of KCCQ TSS.

Updated the information on censoring for the renal endpoint and specifically for the different components.

Clarified intercurrent event strategies for KCCQ responder analyses.

Included thresholds for clinically meaningful change derived from separate anchor analysis.

Clarified analysis of UACR used log-transformation.

Removed breakdown of hospitalizations for DAOH.

Removed MedDRA Labelling Groupings analyses for Adverse events. Included further analyses for AEs by SOC and PT. Included analyses of AEs by subgroups.

The section 6.4.3.3 Further Safety Variables has been integrated into Advere Events Section 6.4.1 with further details included on the definition of Hyperkalemia and Worsening renal function events.

Included display of cumulative incidences for TE hyperkalemia events.

Updated list of lab parameters to be analyzed with geometric statistic (i.e. assuming log-normal data). Included graphical displays for lab parameters.

Included graphical displays for vital signs.

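### The renal on-treatment analysis in SAP 6.2.2.3 has a visit-based window, cites the wrong composite and names no last dose, so how far off drug an event may count is not defined

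*SAP*

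**What the plan says.** SAP 6.2.2.3 opens the topic with "The additional analyses of the secondary time-to-first event endpoints will include an" on-treatment analysis. Under SAP 6.2.2.1 those endpoints are the renal composite and all-cause mortality. For the renal composite, the next sentence restricts counting to events "within 5 months after the last visit with complete information on all components of the composite primary endpoint". The stated reason is: "A 5-month time window is used as visits are 4-monthly and in order to allow for late attendance by an additional 1 month". No date of last dose, treatment stop or analysis set is given.

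Two other places in the SAP define on-treatment for efficacy:

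- Section 4.5.5, for the derived any-time-on-treatment visit: "only assessments on or after study medication start date until 30 days after last study drug administration".
- Section 6.2.1.5, for the primary endpoint: "including only events occurring up to 30 days after treatment discontinuation", followed by "This analysis will be performed in the SAF instead of the FAS".

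The change log in SAP 7.2 records that the on-treatment definition was updated "in general and for renal composite endpoint specifically".

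Participants who stop drug stay in the study. Protocol 1.3 (footnotes to the schedules) and 4.1 keep all randomized participants in follow-up to study end. Central eGFR and endpoint assessment continue under the premature discontinuation schedule (Figure 1–2).

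**The concern.** An on-treatment analysis needs a boundary set by drug exposure. The renal rule supplies one set by attendance, and its rationale (visit spacing plus an allowance for lateness) is about whether an event could have been ascertained. Someone who stopped drug early and kept attending has a late last complete visit, so the rule excludes nothing by reference to the last dose.

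The composite named is also the wrong one. Complete information on CV death and HF events does not establish renal status, because that composite contains no eGFR, dialysis or transplant component.

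What is at stake is interpretation and reproducibility. The same label would carry different meanings for the primary and the renal endpoint, two programmers could derive different renal event sets from the same text, and a renal result labelled on-treatment could include events from far off drug.

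**Working it through.** **The plan's own figure.** A 4-month visit interval plus 1 month gives 4 + 1 = 5 months, so the window reproduces. It fits on-site gaps only after Month 12. In the main schedule (Months 0, 1, 3, 6, 9, 12, then every 4 months) the earlier gaps are 1, 2, 3, 3 and 3 months.

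**The three rules side by side.**

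| SAP section | Anchor | Window | Set |
|---|---|---|---|
| 4.5.5, any time on treatment (efficacy) | last dose | 30 days | not stated there |
| 6.2.1.5, primary endpoint | treatment discontinuation | 30 days | SAF |
| 6.2.2.3, renal composite | last visit complete for the primary composite | 5 months | not stated |

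**One participant.** Drug stopped at Month 6, all visits attended to Month 40. Read literally, renal events count to Month 40 + 5 = Month 45 or end of study, whichever comes first. Under the 30-day rule they count to about Month 7. SAP 6.2.2.1 counts eGFR events from randomization to the end-of-study visit in the main analysis, so for this participant the literal on-treatment window and the main window coincide.

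**How much follow-up is in question (illustration).**

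From the protocol: 5% yearly drug discontinuation (9.2); 24 months' recruitment and 42 months in total (9.2), so follow-up F runs from 18 to 42 months; placebo death parameters 0.005125 + 0.0016 = 0.006725 per month (9.2). From the SAP: about 6000 participants (section 3). Assumed: constant discontinuation hazard, uniform entry, full attendance after stopping, no restarts.

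1. Monthly hazard: λ = −ln(0.95)/12 = 0.004274.
2. Mean probability of still being on drug at the end of follow-up, deaths ignored: M = [exp(−18λ) − exp(−42λ)]/(24λ) = (0.9259 − 0.8357)/0.1026 = 0.880. Share stopping: 1 − 0.880 = 12.0%. With deaths as a competing exit at 0.006725 per month, this is 10.8%.
3. Mean follow-up without deaths: (18 + 42)/2 = 30 months.
4. Mean follow-up on drug or within w = 30/30.4375 = 0.986 months of last dose: w + (1 − M·exp(λw))/λ = 28.18 months.
5. Share beyond last dose + 30 days: 1 − 28.18/30 = 6.1%, which is 0.0606 × 30 × 6000/12 ≈ 909 person-years.
6. Repeating steps 3–5 with deaths gives mean follow-up of 27.04 months, a share of 5.8% and about 784 person-years.

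| Yearly discontinuation | Share beyond last dose + 30 days (with deaths – without) |
|---|---|
| 3% (assumed) | 3.5–3.7% |
| 5% (protocol) | 5.8–6.1% |
| 10% (assumed) | 11.4–11.9% |

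These are shares of follow-up time. The documents give no renal event rate on or off drug, so they cannot be turned into a share of renal events.

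**The case against.** The strongest defence is that the 5-month sentence states a necessary condition. It may be an ascertainment filter laid on top of the 30-day limit, much like the allowance of next planned visit plus 1 month for dialysis and transplant in SAP 6.2.2.1. Two things support this: 6.2.2.3 gives no window at all for all-cause mortality, so that analysis must borrow a definition from elsewhere, and the change log in SAP 7.1 says the on-treatment definitions were aligned throughout. This reading stands as possible. Against it, SAP 7.2 records a renal-specific redefinition, and 6.2.2.3 never refers back to 4.5.5. A reader might therefore infer that the analysis is certainly not limited by last dose. The text does not prove that; it leaves the matter open.

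Referring to the primary composite is probably a one-word slip, since the protocol's renal censoring rule (9.4.1.2) speaks of complete information on the renal composite. Correcting the word would still leave a visit anchor.

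A reader might also infer that renal events on and off drug mean different things because early eGFR falls are reversible (protocol 2.3). The documents do not support this for the endpoint used. The expected eGFR change is 2.4–3.8% (protocol 4.3), while the eGFR components need a fall of at least 50%, or a value below 15, normally confirmed at least 4 weeks later.

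Nor does overlap with the main analysis condemn the rule by itself: a 30-day rule would also keep about 94% of follow-up at 5% a year.

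**Conclusion.** The point holds as a defect of definition. The only renal rule given is a visit-attendance window tied to a composite without renal components, with no last dose and no analysis set. Taken literally it departs from SAP 4.5.5 and 6.2.1.5 and puts no limit on how far off drug an event may be; taken generously it is ambiguous. Counting some off-drug events is not itself the fault, since the 30-day rule does so too.

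About 6% of follow-up is in question at the protocol's discontinuation rate, under the assumptions listed in the check, and about 3.5–12% over the assumed range. It is tempting to add that the share of renal events is higher because falling eGFR prompts stopping. Protocol Table 6–3 does allow interruption when eGFR falls by 40% or more, but nothing in the documents quantifies the effect.

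The analysis is supportive. The confirmatory renal test in SAP 6.2.2.1 and the testing hierarchy in SAP 4.7 are unchanged. It should be corrected, but it does not threaten the trial's main conclusions.

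**What to change.** Rewrite the renal sentence in SAP 6.2.2.3 so that it:

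- counts a renal event if its first qualifying sample, dialysis start or transplant falls within 30 days after the last dose, in line with 4.5.5 and 6.2.1.5;
- names the SAF as the analysis set;
- censors at the earlier of last dose + 30 days and the renal censoring date in 6.2.2.1;
- refers to the renal composite in place of the primary one;
- states the 5-month visit window, if it is kept, only as an additional ascertainment condition.

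The cost is a short SAP edit and one changed derivation. There is one downside: with on-site visits 4 months apart after Month 12, a 30-day limit may miss declines that began on drug but were first sampled at a later visit. If the sponsor prefers a longer window for that reason, it should still run from the last dose and be justified. At 5% yearly discontinuation, a window of last dose + 5 months would leave out about 4.4–4.6% of follow-up, compared with 5.8–6.1% for 30 days.

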#### 8.1.1 Kansas City Cardiomyopathy Questionnaire (KCCQ) and Total Symptom Score (TSS)

The **KCCQ** is a patient-reported disease-specific health status measure intended for the assessment of HF patients' perspectives of how their disease impacts their lives (Green et al. 2000). Patients are asked to recall how their HF impacted their life over a 2-week recall period. Response options for the 23 items (questions) are on a 5- to 7-point Likert-type scale with varying response options depending on the question. It requires, on average, 4 to 6 minutes to complete.

The **TSS** domain of the KCCQ was selected as the secondary endpoint because it is a direct measure of the hypothesized improvement of clinical symptoms. HF symptoms are subjective in nature and are best reported by the patient. The frequency and burden of clinical symptoms of HF in daily life include fatigue (KCCQ items 5 and 6), shortness of breath (KCCQ items 7 and 8), paroxysmal nocturnal dyspnea orthopnea (KCCQ item 9) and patient peripheral edema/swelling (KCCQ items 3 and 4) and are summarized in the TSS.

In addition to the KCCQ TSS, the KCCQ also measures the impact of patients' HF or their treatment in distinct domains: symptoms (with subscores for frequency and burden), physical limitations, quality of life, social limitations, self-efficacy and symptom stability. All scores are transformed to a 0-100 scale, with higher scores indicating a better outcome. The domains of self-efficacy (a measure of patient knowledge of preventing HF exacerbations) and symptom stability (a measure of symptom change over the previous 2 weeks) will not be considered measures of treatment efficacy.

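### The floor clause in the KCCQ no-deterioration analysis is either wrong or redundant, and the anchor-based responder analysis omits the ceiling clause without saying whether that is intended

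*SAP*

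**What the plan says.** Section 6.2.2.3 of the SAP describes two sets of KCCQ TSS responder analyses.

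- **First set, improvement.** Response is a gain of at least 5, 10 or 20 points by Month 12, and each cut-off has a ceiling clause. At 5 points, someone starting above 95 responds with "a score of >95 at Month 12 without decline from baseline) as a responder". The 10 point clause uses 90. At 20 points the clause reads "or maintaining a score of >80 without decrease from baseline".
- **First set, no deterioration.** A responder is someone without a fall of 5 points or more. A parenthesis introduced by *or* says that those with a baseline below 5 need a Month 12 score of at least 5. The SAP then comments: "This is equivalent to not experiencing a small deterioration".
- **Second set, anchor-based.** The thresholds are 9.09 for minimal improvement and, for the next level, "Moderate within-patient improvement: 19.85". At Months 6, 9 and 12, "These thresholds will be used for each timepoint". The SAP restates the use of observed data, the rule for missing scores, death as non-response, and a logistic model with baseline TSS as a covariate. It gives no ceiling clause.

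On the scale itself, protocol section 8.1.1 says: "All scores are transformed to a 0-100 scale, with higher scores indicating a better outcome".

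**The concern.** A fall of 5 points is impossible from a baseline below 5, so nobody in that group can show a small deterioration as the SAP defines it. A clause that nevertheless asks them to reach 5 can turn stable or improving participants into failures. Two programmers could also code it differently.

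In the anchor-based set, participants who start near the top of the scale cannot respond whatever happens to them. The first set treats the same people as potential responders at nearly the same cut-offs. The two planned results could therefore disagree for a reason unrelated to treatment. KCCQ TSS is in the formal testing hierarchy (SAP section 4.7), so readers will look to these percentages when judging what a mean difference is worth.

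**Working it through.** **1. The plan's own ceilings.** TSS runs from 0 to 100, so the ceiling is 100 minus the cut-off: 100 − 5 = 95, 100 − 10 = 90, 100 − 20 = 80. All three match the SAP.

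**2. The same arithmetic for the anchor thresholds.** 100 − 9.09 = 90.91 and 100 − 19.85 = 80.15. No response is possible from a baseline above these values.

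**3. Attainable scores.** SAP appendix 9.1 makes TSS the mean of the frequency and burden scores. With complete questionnaires:
- one step on question 3 or 9 moves TSS by 100/(4·4·2) = 3 units of 100/96;
- one step on question 5 or 7 moves it by 100/(6·4·2) = 2 units;
- one step on a burden item moves it by 100/(3·4·2) = 4 units.

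Every value from 0 to 96 units can be reached except 1 and 95, which leaves 95 values.

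**4. Floor clause.** The attainable values below 5 are 0, 2.08, 3.12 and 4.17, giving 4 × 4 = 16 baseline/Month 12 pairs that stay below 5.
- *Parenthesis replaces the main rule:* all 16 are non-responders. Four are unchanged, six improved (for example 0 to 4.17) and six fell by at most 4.17. None fell by 5.
- *Parenthesis is a plain alternative:* all 16 already respond under the main rule, and no classification changes anywhere on the scale.

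**5. Ceiling.** Nineteen units are 19.79 points and twenty are 20.83, so no attainable change lies between 19.85 and 20. The same 19 values lie above 80 and above 80.15 (the lowest is 80.21). At Month 12 the two analyses also share the model and the rules for missing scores and death. With complete questionnaires they therefore differ only by the ceiling clause. Example: 85.42 to 100 is a gain of 14.58, a response at 20 points (score kept above 80) but not at 19.85. Eight values lie above 90.91 (the lowest is 91.67). The 9.09 and 10 point change criteria also differ for the single change of 9 units, 9.375 points.

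**6. Size.** The documents give no TSS distribution, so everything here is assumed.

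| Assumed baseline | Above 90.91 | Above 80.15 | Below 5 |
|---|---|---|---|
| Normal truncated to 0–100, mean 60–75, SD 20–24 | 4–12% | 14–33% | 0.5% or less |
| Normal clipped at 0 and 100, mean 60–70, SD 22–24 | 8–19% | 18–34% | 0.2–1.1% |

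Simulation: clipped normal, n = 5400, SD 24, correlation 0.65, placebo gain 4 points, treatment effect 2 points, logistic model with treatment and baseline, 100 replicates. Each cell reads without → with the ceiling clause.

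| Baseline mean, threshold | Odds ratio | Difference (points) | Placebo responders | Mean z |
|---|---|---|---|---|
| 60, 9.09 | 1.19 → 1.19 | 3.5 → 3.9 | 39% → 42% | 2.9 → 3.0 |
| 60, 19.85 | 1.20 → 1.18 | 2.6 → 3.5 | 20% → 28% | 2.6 → 2.8 |
| 70, 9.09 | 1.19 → 1.18 | 3.3 → 4.0 | 37% → 46% | 2.8 → 3.0 |
| 70, 19.85 | 1.19 → 1.17 | 2.2 → 3.6 | 19% → 34% | 2.3 → 2.8 |

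In the same runs, 0.17% (mean 60) and about 0.03% (mean 70) of participants were below 5 at both times, the only group the floor clause can misclassify.

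**The case against.** **On the floor.** The text says *or*. Taken literally, everyone below 5 already qualifies, the SAP's comment on the meaning is true, and nobody is misclassified. That reading is available, but it leaves the clause without any function. The SAP's list of reasons for non-response also splits participants by baseline (above 95 at baseline, 95 or lower afterwards), which points to replacement. A deliberate mirror of the ceiling rule is conceivable too. The ceiling rule, however, has a no-decline condition, and the floor clause has no counterpart that would spare someone who improved.

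**On the ceiling.** The thresholds are labelled as within-patient improvement, and 98 to 98 is not an improvement. The SAP also plans a version with ceiling clauses, a breakdown of the criteria met, and distribution curves of change by arm, so a reader can trace any discrepancy. Adding the clause has costs. At Month 12 it would make the 19.85 analysis a duplicate of the 20 point one for complete questionnaires. It would also create a jump: a baseline of 79.17 must reach 100, while 80.21 need only not fall. These arguments stand, and they make the omission a choice of definition. It is less convincing that the clauses carry over unstated, since the SAP restates the other rules for this analysis and gives no limit of 90.91 or 80.15.

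**What a reader might infer.** One could conclude that the missing clause understates the treatment effect, or that this analysis is the main aid to interpreting the endpoint. The documents support neither. The planned measure is a baseline-adjusted odds ratio, which the simulation shows is not lowered by the omission. The SAP presents this as a second responder analysis among the supportive ones, outside the hierarchy.

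**Conclusion.** The floor parenthesis is defective on either reading and should go, although its effect is very small: well under 1% of participants under the assumed distributions.

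The missing ceiling clause is a matter of definition that the SAP should state openly. It lowers responder percentages and absolute differences, and in the simulation it lowers the mean z by about 0.1 to 0.5, but no confirmatory test uses that z. The limit applies equally to both arms, so it does not bias the comparison. The limits 90.91 and 80.15 and the match between 19.85 and 20 follow from the scoring rules, the latter for complete questionnaires only. The shares and simulated effects depend on the assumed TSS distribution, correlation and gains. Overall this is a minor clarification.

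**What to change.** 1. **No-deterioration analysis:** delete the parenthesis about baselines below 5. Participants starting there then count as not deteriorated, which matches the stated meaning.
2. **Anchor-based analysis:** keep the pure-change definition, add a sentence saying that no ceiling clause applies by design, and report per arm how many participants have a baseline above 90.91 and above 80.15.
3. **Optional companion, not a replacement:** repeat the analysis counting as responders those with a baseline above 90.91 (or 80.15) who stay above it without decline. At 19.85 and Month 12 this adds nothing to the 20 point analysis when questionnaires are complete, so it is informative mainly at 9.09 and at Months 6 and 9.

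The cost is one deletion, one or two sentences and one extra table row. No new data are needed. The companion would count maintained high scores as response, a convention that the first set already uses.
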